8.2.3. Subject Incidence of Adverse Events

Summaries will be displayed by SOC and PT, and will be ordered by descending order of overall incidence of system organ class and preferred term within each system organ class. Summaries of the following types will be presented:

- Subject incidence of TEAEs by MedDRA SOC and PT.
- Subject incidence of TEAEs by MedDRA PT.
- Subject incidence of TE AESIs by AESI Category MedDRA PT.
- Subject incidence of TEAEs by MedDRA SOC, PT, and highest severity (CTCAE grade). At each level of subject summarization, a subject is classified according to the highest severity if the subject reported 1 or more events. AEs with missing severity (CTCAE grade) will be considered Grade 3 (severe) for this summary.
- Subject incidence of CTCAE Grade 3 or higher TEAEs by MedDRA SOC and PT. At each level of subject summarization, a subject is classified according to the highest severity if the subject reported 1 or more events. AEs with missing severity (CTCAE grade) will be considered Grade 3 (severe) for this summary.
- Subject incidence of treatment-related TEAEs by MedDRA SOC and PT. Related AEs are those with relationships reported as “Related” or “Possibly Related”. At each level of subject summarization, a subject is classified according to the closest

relationship to study drug if the subject reported 1 or more events. AEs with a missing relationship will be considered related for this summary.

- Subject incidence of treatment-related CTCAE Grade 3 or higher TEAEs by MedDRA SOC and PT. At each level of subject summarization, a subject is classified according to the highest severity if the subject reported 1 or more events. AEs with missing severity (CTCAE grade) will be considered Grade 3 (severe) for this summary. AEs with a missing relationship will be considered related for this summary.
- Subject incidence of serious TEAEs by MedDRA SOC and PT.
- Subject incidence of serious TEAEs by MedDRA PT.
- Subject incidence of TEAEs leading to any study drug modification (reduced, interrupted, discontinued) by MedDRA SOC and PT. This is a subset of the AEs where Action Taken with Study Drug is checked as “Drug Withdrawn.”, “Dose Reduced”, or “Drug Interrupted”.
 - Subject incidence of TEAEs leading to study drug discontinued by MedDRA SOC and PT. This is a subset of the AEs where Action Taken with Study Drug is checked as “Drug Withdrawn.”
 - Subject incidence of TEAEs leading to dose reduction by MedDRA SOC and PT. This is a subset of the AEs where Action Taken with Study Drug is checked as “Dose Reduced.”
 - Subject incidence of TEAEs leading to study drug interruption by MedDRA SOC and PT. This is a subset of the AEs where Action Taken with Study Drug is checked as “Drug Interrupted.”

The above summaries will be repeated where the adverse event is assigned to the dose the subject was taking at the time of the adverse event.

The following listings will be presented by treatment group and subject, include study day event started and the duration of event:

- All adverse events.
- AESIs (subset of the AEs where AE of Special Interest is marked as “Yes” or the AE meets the criteria specified in [Section 8.2.1](#)).
- Serious adverse events (subset of the AEs where serious is marked as “Yes”).
- CTCAE Grade 3 or higher adverse events (subset of AEs where severity is marked as CTCAE Grade 3, 4, or 5 or missing [to be presented as missing on the listing]).
- Related adverse events (subset of the AEs where relationship marked as “Related” or “Possibly Related” or missing relationship [to be presented as missing on the listing]).
- Adverse events leading to dose reduction (subset of the AEs where Action Taken with Study Drug is checked as “Dose Reduced”).

- Adverse events leading to study drug interruption (subset of the AEs where Action Taken with Study Drug is checked as “Drug Interrupted”).
- Adverse events leading to study drug discontinued (subset of the AEs where Action Taken with Study Drug is checked as “Drug Withdrawn”).
- Adverse events leading to discontinuation from the study (subset of the AEs where “Did the adverse event cause the subject to be discontinued from the study?” is “Yes”)
- Adverse events leading to death (subset of the AEs where outcome is indicated as “Fatal” or the CTCAE grade is 5 or seriousness criteria is Death).

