4.4.1.1. Diarrhea

In the event the patient experiences diarrhea, the dose may be reduced. The Common Terminology Criteria for Adverse Events (CTCAE) version 4.0 grading will be used to grade the severity of all AEs and serious adverse events (SAEs) of diarrhea. Management recommendations for diarrhea are based on the CTCAE grades and are detailed in Appendix 2. In general, the patient should be treated with anti-diarrheal drugs such as loperamide as clinically indicated. In addition to directly treating any diarrhea, possible intermittent or permanent interruption of IP and dose reduction will be possible, depending upon the frequency and severity of diarrhea.

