10.1. Statistical Hypotheses

No formal hypotheses are planned for the study.

10.2. **Sample Size Determination**

The sample size for this study was not based on a formal hypothesis testing. It is expected that 30 patients per arm will provide sufficient data to assess the safety and efficacy. Power calculations were conducted to examine the probability of detecting a difference among treatment groups for the percentage change of PVR from baseline.

A sample size of 90 patients with 30 patients to be randomized into 1 of the 3 treatment arms in a 1:1:1 randomization is planned. A sample size of 30 patients per arm will provide at least 80% power at a significance level of 0.05 (2-sided hypothesis) to detect a treatment difference of 0.75 times of standard deviation (SD) in the percentage change from baseline of PVR from baseline between an active arm and the placebo arm. If the SD for PVR percent change is 24%, the study has 80% power to detect a difference of 18% between an active arm and the placebo arm.

10.3. **Populations for Analyses**

For purposes of analysis, the following populations are defined:

Population	Description
Enrolled	All patients who sign the ICF
Intent-to-Treat (ITT)	All patients randomized into the study. For all summaries based on the ITT population, patients will be assigned to the treatment arm to which they were randomized.
Modified Intent-to-Treat (m-ITT):	All safety population patients that had an evaluable baseline and completed at least 1 post-baseline efficacy assessment. Patients will be analyzed according to the treatment they actually received.
Per Protocol (PP)	All m-ITT population patients who had no major protocol deviations and completed the Week 24 visit.
Safety	All patients randomly assigned to IP and who take at least 1 dose of IP. Patients will be analyzed according to the treatment they actually received.

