5. Is a congenital anomaly/birth defect

6. Other situations:

- Medical or scientific judgment should be exercised in deciding whether SAE reporting is
 appropriate in other situations such as important medical events that may not be immediately life
 threatening or result in death or hospitalization but may jeopardize the patient or may require
 medical or surgical intervention to prevent one of the other outcomes listed in the above definition.
 These events should usually be considered serious.
- Examples of such events include invasive or malignant cancers, intensive treatment in an emergency room or at home for allergic bronchospasm, blood dyscrasias, or convulsions that do not result in hospitalization, or development of drug dependency or drug abuse.

Recording and Follow Up of Adverse Events and/or Serious Adverse Events

Adverse Event and Serious Adverse Event Recording

- When an AE/SAE occurs, it is the responsibility of the Investigator to review all documentation (e.g., hospital progress notes, laboratory reports, and diagnostics reports) related to the event.
- The Investigator will then record all relevant AE/SAE information in the case report form.
- It is not acceptable for the Investigator to send photocopies of the patient's medical records to Sponsor in lieu of completion of the AE/SAE case report form page.
- There may be instances when copies of medical records for certain cases are requested by Sponsor. In this case, all patient identifiers, with the exception of the patient number, will be redacted on the copies of the medical records before submission to Sponsor.
- The Investigator will attempt to establish a diagnosis of the event based on signs, symptoms, and/or other clinical information. Whenever possible, the diagnosis (not the individual signs/symptoms) will be documented as the AE/SAE.

Assessment of Intensity

The Investigator will make an assessment of intensity for each AE and SAE reported during the study and assign it to 1 of the following categories:

- Mild: An event that is easily tolerated by the patient, causing minimal discomfort, and not interfering with everyday activities.
- Moderate: An event that causes sufficient discomfort and interferes with normal everyday activities.

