8. SAFETY ANALYSES

Safety analyses will be conducted using the Safety population.

No inferential comparison of safety endpoints will be performed.

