8.2. Adverse Events

Adverse events will be coded using Medical Dictionary for Regulatory Activities (MedDRA) each verbatim term coded to a lower level term (LLT) which is mapped to a preferred term (PT), high level term (HLT), high level group term (HLGT), and a system organ class (SOC). AE severity and intensity using the National Cancer Institute Common Terminology Criteria for Adverse Events (NCI CTCAE, Version 5) are recorded on the eCRF. Both will be presented in listings, CTCAE grade will be used in summaries and analyses.

Adverse event summaries will summarize only treatment-emergent AEs (TEAEs), which are defined as AEs not present prior to the start of study medication, or AEs present before study medication that worsened after starting study medication. If a partially missing date or time of onset allows the possibility that an AE may be a TEAE it will be assumed that it is a TEAE. Each AE will be assigned to the most recent treatment received AEs with a start on or after the first OLE dose will be assigned to the OLE treatment phase and not included in the main study AE analyses. For subjects who discontinued study without going to the open label extension, AEs started after first dose and within the 28 days of last dose will be counted as TEAEs. If it cannot be determined whether an AE is treatment emergent due to a partial onset date, then it will be counted as such. Methodology for imputation of partial AE start and stop dates is described in [Appendix 1](#). Each summary will be displayed by treatment group, including Total Rodatristat ethyl and Overall.

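### SAP 8.2.3 counts an AE with no CTCAE grade as Grade 3 without first using the investigator's recorded severity, and SAP 8.2.2 and Table 12 state no rule for a missing grade

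*SAP*

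**What the plan says.** SAP 8.2 describes two assessments on the eCRF, a severity rating and a CTCAE version 5 grade, and gives them different uses: "Both will be presented in listings, CTCAE grade will be used in summaries and analyses". The sentence is terse, but its wording implies two separate fields.

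SAP 8.2.3 then deals with a blank grade: "AEs with missing severity (CTCAE grade) will be considered Grade 3 (severe) for this summary". This sentence is attached to three tables: TEAEs by highest severity, Grade 3 or higher TEAEs, and treatment-related Grade 3 or higher TEAEs. The same section repeats its summaries by the dose being taken when the event began, so the rule carries into those repeats. The Grade 3+ listing covers events where "severity is marked as CTCAE Grade 3, 4, or 5 or missing [to be presented as missing on the listing".

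Protocol Appendix 14 tells the investigator to "make an assessment of intensity for each AE and SAE reported during the study and assign it to 1 of the following categories", and the categories are mild, moderate and severe. Among clinical events, the protocol's explicit instruction to grade by CTCAE is for diarrhea, in Section 4.4.1.1: "version 4.0 grading will be used to grade the severity of all AEs and serious adverse events (SAEs) of diarrhea". Appendix 3 attaches CTCAE grades to liver enzyme elevations.

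SAP 8.2.2 tabulates Grade 3+ TEAEs, TEAEs by maximum grade and related Grade 3+ TEAEs. SAP Table 12 defines four AESI categories by a minimum grade of 2 or 3. Neither place says what to do when the grade is missing.

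**The concern.** Worst-case imputation is reasonable when nothing is known about an event's severity. Here something normally is known, because the protocol requires a rating for every event. As written, the rule replaces an investigator's rating of mild with Grade 3 whenever the second field is blank. The table then contradicts the trial's own data.

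With about 30 patients per arm, each patient wrongly counted moves an arm's incidence by 1/30 = 3.3 points. In a dose-ranging trial, readers will compare the severe-event columns across doses, so one or two such patients would be noticeable.

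The second issue is consistency. The closing words of the rule confine it to the table at hand. An overall Grade 3+ count from 8.2.2 and the corresponding count from 8.2.3 can therefore differ for the same patients.

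**Working it through.** **No figure to reproduce.** Neither document gives a missing-grade rate, an AE rate by arm or an expected Grade 3+ rate. The check is a reading of the text, followed by an illustration whose inputs are assumptions.

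**Step 1: follow one event through the tables.** Take a treatment-emergent nausea event rated mild, with no CTCAE grade.

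| Place in SAP | Treatment of the event |
|---|---|
| 8.2, listings | Both fields shown: mild, grade blank |
| 8.2.3, highest severity | Grade 3 |
| 8.2.3, Grade 3+ | Counted |
| 8.2.3, related Grade 3+ | Counted if related, possibly related or relationship missing |
| 8.2.3, repeats by dose at onset | As in the three rows above |
| 8.2.3, Grade 3+ listing | Included, grade shown as missing |
| 8.2.2, Grade 3+, maximum grade, related Grade 3+ | No rule |
| Table 12, nausea and vomiting at Grade 3+ | No rule |

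The rule is not uniformly conservative either. A fatal event with a blank grade becomes Grade 3 in the highest-severity table, although the 8.2.3 listing of deaths would identify it from its outcome or seriousness criterion.

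**Step 2: illustrate the size.** Let m be the share of AEs with no grade, k the number of non-severe AEs per patient, and p the true share of patients with a Grade 3+ event. If grades are missing independently from event to event, the added share of patients counted as Grade 3+ is

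(1 − p) × [1 − (1 − m)^k].

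This is for the row counting any Grade 3+ event. All of m, k and p are assumed; only the 30 patients per arm comes from the plan (Protocol 10.2). With p = 10% in both arms:

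| m | k = 2 | k = 4 | Patients of 30 |
|---|---|---|---|
| 0% | 0 | 0 | 0 vs 0 |
| 1% | 1.8 points | 3.5 points | 0.5 vs 1.1 |
| 2% | 3.6 points | 7.0 points | 1.1 vs 2.1 |
| 5% | 8.8 points | 16.7 points | 2.6 vs 5.0 |

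Worked line for m = 2%: 0.9 × (1 − 0.98²) = 0.9 × 0.0396 = 3.6 points; 0.9 × (1 − 0.98⁴) = 0.9 × 0.0776 = 7.0 points.

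**Step 3: test whether the direction by arm is fixed.** It is not.

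- Different true rates: at m = 2%, k = 2 with p = 10% gives 3.6 points. With k = 3 and p = 45% it is 0.55 × (1 − 0.98³) = 3.2 points, so the arm with fewer events gains more.
- Different missingness: m = 5% with k = 2 gives 8.8 points, and m = 1% with k = 4 gives 3.5 points (p = 10% in both).
- Clustered missingness: if 5% of patients have every grade blank and everyone has at least one AE, the added share is 0.9 × 5% = 4.5 points in both arms, whatever k is.
- Risk ratio: with true rates of 10% and 20%, k = 2 and 4, and m = 5%, the apparent rates are 18.8% and 34.8%. The risk difference rises from 10.0 to 16.1 points while the risk ratio falls from 2.00 to 1.86.

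**Step 4: apply recorded severity first.** Events rated mild or moderate then map to Grade 1 or 2, and their contribution to the Grade 3+ count is zero for any m, k and p.

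**The case against.** The case for leaving the rule alone has several sound parts.

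- Nothing in the documents shows that any grade is missing. SAP 8.2 has the CTCAE grade recorded on the eCRF for AEs in general, and Protocol 7.3.1 uses Grade 3 or 4 AEs as an extension-phase endpoint.
- SAP 7.1.3.3 holds database lock until data problems found during programming are resolved. A blank grade beside a completed severity rating is an obvious query.
- The rule fits the SAP's other cautious defaults: a missing relationship counts as related, and an uncertain onset date counts as treatment-emergent.
- The imputation can be traced, because listings show both fields and the Grade 3+ listing leaves the grade blank. The comparisons are descriptive: "No inferential comparison of safety endpoints will be performed".

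A reader might go further and infer that the severe-AE tables are inflated, most of all in the arm with most events, so that a false dose-related signal is built in. The documents do not support that. It needs missing grades, which are not reported. It also needs missingness that is similar across arms and independent between events, and AE counts by arm that are not given. If whole sites or patients were ungraded, missingness would cluster and the arm contrast would shrink. Protocol 4.7 names nausea and diarrhea as the dose-dependent gastrointestinal events, but diarrhea is the event the protocol explicitly requires to be graded, so it is among the least likely to lack a grade.

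These points limit the size of the problem. They do not explain why a recorded rating should be passed over, and listings do not reconcile incidence tables that follow different rules.

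**Conclusion.** The point holds as a conditional defect. SAP 8.2.3 can override a severity rating that the protocol requires, and it does so in three tables and their repeats by dose at onset. If any event rated mild or moderate lacks a grade at lock, those tables would overstate severe-event incidence. Separately, the missing rule in 8.2.2 and Table 12 means that Grade 3+ counts can disagree between tables.

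The size is unknown: zero with complete grades, and about one to two patients of 30 at 2% missing under the independence model and assumed event counts above. The direction by arm is also unknown. Confidence is high on what the rule says and on the gap between sections. The practical impact depends on a number the documents do not give.

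**What to change.** State one rule and apply it in SAP 8.2.2, 8.2.3 and Table 12:

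1. Query blank CTCAE grades before database lock.
2. If a grade is still missing, assign it from recorded severity: mild = 1, moderate = 2, severe = 3, and fatal outcome = 5.
3. Use Grade 3 only when both fields are missing.
4. Footnote, by arm, how many AEs were assigned a grade by each route.

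The worst-case default remains where nothing is known. The cost is a short SAP amendment and one derivation, with no new data. The downside is that it maps one severity scale onto another. In particular, an ungraded event rated severe cannot be separated into Grade 3 or Grade 4. That leaves the Grade 3+ counts unchanged but can affect the maximum-grade table, and the footnote makes it visible.

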8.3. Clinical Safety Laboratory Evaluations

Hematology, clinical chemistry, coagulation, urinalysis, and additional laboratory parameters to be tested are provided in section 9.2.5 of the protocol. All clinical laboratory data will be presented in by-subject data listings using standard international (SI) system of units.

In general, clinical safety laboratory evaluations were assessed via a central laboratory. However, in some cases, a local laboratory was used for repeat assessments or when the appropriate central lab kit was not available. Local labs are recorded on an Unscheduled CRF and will be windowed according to [Section 4.7.1](#). For the purposes of summaries, if a central laboratory result is available in the analysis visit window ([Section 4.7.1](#)), it will be used for analyses. If not central laboratory result is available, and a local laboratory result is available within the visit window, it will be used for summaries. Local labs without a unit will be excluded.

The following laboratory tests will be presented in listings only: Direct Bilirubin, Lipase, Urinalysis, FSH, Pregnancy testing (hCG), and drugs of abuse. Estimated glomerular filtration rate (eGFR) will be summarized with the chemistry panel.

Continuous laboratory results and changes from baseline will be summarized descriptively. All clinical laboratory data will be presented in by-subject data listings with local laboratory results flagged. Values outside of the laboratory’s reference range (ie, those with high or low values) will be flagged in the laboratory listings. The CTCAE grade will also be included in the listings. A separate listing for laboratory normal ranges, by lab category, lab test, sex, and age, will be presented.

8.3.1. Treatment Emergent Abnormalities

Quantitative laboratory values will be assigned grades according to the National Cancer Institute (NCI) Common Terminology Criteria for Adverse Events (CTCAE) version 5.0, where applicable.

For each applicable laboratory test, a treatment emergent abnormality will be defined as a post-baseline, through Follow-Up (Week 28) or prior to first dose in the OLE phase, CTCAE grade increase of ≥ 2 grades and any CTCAE grade 3 or 4.

The number and percentage of subjects overall and by laboratory test, with any treatment emergent laboratory abnormality, CTCAE increase of ≥ 2 grades, will be presented.

A separate data listing of treatment emergent Grade 3 and Grade 4 laboratory abnormalities or increase of ≥ 2 grades will also be provided.

8.3.2. Shifts in CTCAE Grade

Shifts in CTCAE grade of laboratory tests will be presented from baseline to worst post-baseline value and at each post-baseline visit. Summaries will present the number and percentage of subjects with shifts in laboratory grade by treatment group. Denominators for percentages will be the number of subjects with non-missing data at the specific assessment and baseline.

Some lab tests include additional clinical criteria which cannot be determined programmatically. **Table 13** below specifies the grade with clinical criteria in italics. The text in italics will not be considered when assigning grades programmatically.

Table 13: CTCAE Laboratory Tests with Clinical Criteria

Amylase (serum amylase increase)

Grade 1: $>\text{ULN} - 1.5 \times \text{ULN}$Grade 2: $>1.5 \times \text{ULN} - 2.0 \times \text{ULN}$; $>2.0 - 5.0 \times \text{ULN}$ and asymptomaticGrade 3: $>2.0 - 5.0 \times \text{ULN}$ with signs or symptoms; $>5.0 \times \text{ULN}$ and asymptomaticGrade 4: $>5.0 \times \text{ULN}$ and with signs or symptoms
Bicarbonate (Blood bicarbonate decreased): 
Grade 1: $<\text{LLN}$ and no intervention initiated.
Prothrombin Time (PT)/International Normalized Ratio (INR) (INR increased): 
Grade 1: $>1.2 - 1.5$; $>1 - 1.5 \times \text{baseline}$ if on anticoagulation; monitoring only indicatedGrade 2: $>1.5 - 2.5$; $>1.5 - 2.5 \times \text{baseline}$ if on anticoagulation; dose adjustment indicatedGrade 3: >2.5; $>2.5 \times \text{baseline}$ if on anticoagulation; bleeding
eGFR (Chronic Kidney Disease): 
Grade 4: $<15 \text{ ml/min}/1.73\text{m}^2$; dialysis or renal transplant indicated
Glucose (Hypoglycemia): 
Grade 4: $<30 \text{ mg/dL}$; $<1.7 \text{ mmol/L}$; life-threatening consequences; seizures.
Potassium (Hypokalemia) 
Grade 2: Symptomatic with $<\text{LLN} - 3.0 \text{ mmol/L}$; intervention indicatedGrade 3: $<3.0 - 2.5 \text{ mmol/L}$; hospitalization indicatedGrade 4: $<2.5 \text{ mmol/L}$; life-threatening consequences
Potassium (Hyperkalemia)


• Grade 2: >5.5 - 6.0 mmol/L; intervention initiated• Grade 3: >6.0 - 7.0 mmol/L; hospitalization indicated• Grade 4: >7.0 mmol/L; life-threatening consequences
Sodium (Hyponatremia) 
• Grade 2: 125-129 mmol/L and asymptomatic• Grade 3: 125-129 mmol/L symptomatic; 120-124 mmol/L regardless of symptoms• Grade 4: <120 mmol/L; life-threatening consequences
Sodium (Hypernatremia) 
• Grade 2: >150 - 155 mmol/L; intervention initiated• Grade 3: >155 - 160 mmol/L; hospitalization indicated• Grade 4: >160 mmol/L; life-threatening consequences
Albumin (Hypoalbuminemia) 
• Grade 4: Life-threatening consequences; urgent intervention indicated.

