8.3.3. Special Assessments of Potential Hepatotoxicity

The number and percentage of subjects who met the criteria in [Table 14](#), based on their maximum post-baseline value, will be presented to assess any potential for drug-induced hepatotoxicity or liver injury per Guidance for Industry: Drug Induced Liver Injury: Premarketing Clinical Evaluation, CDER, FDA (2009).

Table 14: Hy's Rule Laboratory Abnormalities

Hepatocellular Injury and Liver Function Tests	Range of Test Values
AST	3 to <5 × ULN
	5 to <10 × ULN
	10 to <20 × ULN
	≥20 × ULN
	>2 × Baseline
ALT	3 to <5 × ULN
	5 to <10 × ULN
	10 to <20 × ULN
	≥20 × ULN
	>2 × Baseline
AST or ALT	3 to <5 × ULN

Hepatocellular Injury and Liver Function Tests	Range of Test Values
	5 to $<10 \times$ ULN
	10 to $<20 \times$ ULN
	$\geq 20 \times$ ULN
	$>2 \times$ Baseline
Total bilirubin	$>$ ULN
	$>1.5 \times$ ULN
	$>2 \times$ ULN
Alkaline phosphatase	$>1.5 \times$ ULN
	$>2 \times$ ULN
AST or ALT plus total bilirubin	$>3 \times$ ULN (AST or ALT) plus $>1.5 \times$ ULN Total Bilirubin, and ALP $<2 \times$ ULN
AST or ALT plus total bilirubin	$>3 \times$ ULN (AST or ALT) plus $>2 \times$ ULN (Total Bilirubin, and ALP $<2 \times$ ULN

ALT = alanine aminotransferase; AST = aspartate aminotransferase; ULN = upper limit of normal

eDISH (evaluation of Drug-Induced Serious Hepatotoxicity) plots will be provided for the maximum AST/ALT post baseline vs the maximum total bilirubin post baseline. Similarly eDISH plots for the maximum AST/ALT post baseline vs the maximum GGT post baseline will be provided.

The mean values and mean change from baseline in GGT, AST, and ALT will be plotted by treatment group over time. The same plots will be generated in units of ULN.

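### Three laboratory-summary rules in SAP 8.3 (grade overlaps, the treatment-emergent definition, and unlinked liver maxima) leave counts undetermined or can misclassify patients

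*SAP*

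**What the plan says.** **Grading (SAP 8.3.2, Table 13).** Some CTCAE laboratory grades carry clinical criteria that a program cannot judge. Table 13 prints these in italics and the SAP states: "The text in italics will not be considered when assigning grades programmatically". For low sodium and for amylase, only the symptom words are italic, so the numeric range beside them stays in force. For low sodium, Grade 2 is 125-129 mmol/L, and the next grade opens with the same range ("Grade 3: 125-129 mmol/L") before adding 120-124 mmol/L.

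**Treatment-emergent abnormality (SAP 8.3.1).** The definition is a post-baseline rise of at least 2 "grades and any CTCAE grade 3 or 4". The summary table is then described by a rise of at least 2 grades alone. The listing is described as treatment-emergent Grade 3 and 4 abnormalities *or* a rise of at least 2 grades.

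**Combined liver rows (SAP 8.3.3, Table 14).** Patients are counted against the Table 14 criteria "based on their maximum post-baseline value". Two rows combine AST or ALT above 3 times ULN, total bilirubin (above 1.5 times ULN in one row, above 2 times in the other) and ALP below 2 times ULN. Nothing requires the three results to come from the same sample or from a stated window.

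**The concern.** Two programmers could follow the SAP faithfully and produce different counts. The first needs to know which grade a sodium of 127 mmol/L receives; the second needs to know whether a worsening from Grade 2 to Grade 3 is treatment-emergent. The SAP settles neither.

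The liver rows raise a different problem. The rule there is clear enough to program, but it can classify a patient against the purpose of the row. The ALP condition is an upper limit, so taking the ALP maximum over the whole period lets a rise at any other visit remove a patient whose transaminases and bilirubin were raised together while ALP was low.

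These analytes matter in this trial. Diarrhea and hepatic enzyme elevation are both adverse events of special interest (Protocol 9.3.1). Electrolyte imbalance is part of the diarrhea assessment (Protocol Appendix 2) and of the QT risk mitigation (Protocol 2.3).

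**Working it through.** There is no design figure to reproduce. The check is a logical reading of the three rules.

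**1. Overlaps once the italic text is removed (inputs: Table 13).**

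| Test and value | Numeric criteria met | Grades |
|---|---|---|
| Amylase 3 × ULN | above 2 to 5 × ULN | 2 and 3 |
| Amylase 6 × ULN | above 5 × ULN | 3 and 4 |
| Sodium 127 mmol/L | 125-129 | 2 and 3 |
| Sodium 122 mmol/L | 120-124 | 3 only |

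The ranges printed for high sodium, low potassium (lower limit of normal assumed to be 3.5 mmol/L), high potassium and absolute INR gave one grade per value tested. The double grading is therefore confined to amylase and low sodium. The choice changes the count: amylase rising from 1.2 × ULN (Grade 1) to 3 × ULN is 2 − 1 = +1 or 3 − 1 = +2, so it falls outside or inside the table of rises of at least 2 grades.

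**2. Treatment-emergent wording (inputs: SAP 8.3.1).** Baseline and post-baseline grades each run 0 to 4, giving 5 × 5 = 25 pairs.

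| Rule | Qualifying pairs | Number |
|---|---|---|
| Definition, strict *and*: rise ≥ 2 and Grade 3/4 | 0→3, 0→4, 1→3, 1→4, 2→4 | 5 |
| Table: rise ≥ 2 | the above plus 0→2 | 6 |
| Listing, *or*, worsening to Grade 3/4 required | the above plus 2→3, 3→4 | 8 |
| *Or* with any Grade 3/4, worsened or not | the above plus 3→3, 4→3, 4→4 | 11 |

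The *and* could instead mean that both categories count. That reading does not reconcile the text: the definition then gives 8 or 11 pairs against the table's 6. On either reading, 2→3 and 3→4 lie outside the tabulated count.

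**3. Maxima against same-visit values (inputs: the Table 14 combined rows; two invented patients, values in multiples of ULN).**

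| Patient | Visit 1 (ALT, bilirubin, ALP) | Visit 2 | Maxima | By maxima | Same visit |
|---|---|---|---|---|---|
| A | 4, 1, 1 | 1, 2.5, 1 | 4, 2.5, 1 | counted | not counted |
| B | 4, 2.5, 1 | 1, 1, 2.3 | 4, 2.5, 2.3 | not counted (2.3 is not < 2) | counted at Visit 1 |

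Bilirubin of 2.5 passes both the 1.5 and the 2 thresholds, so the result is the same in both combined rows. Unlinked maxima can misclassify in either direction.

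**Size.** With 30 patients planned per arm (SAP 3), one reclassified patient is 1/30 = 3.3 percentage points.

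**The case against.** The strongest reply is that little is hidden. Ignoring the italic text is a disclosed simplification. The shift tables show baseline to worst grade and to each visit, so 2→3 and 3→4 worsening is tabulated by arm, and the 8.3.1 listing also includes it. Patient B above still appears in the single-analyte rows of Table 14 and on the eDISH plot of maximum AST/ALT against maximum bilirubin, which has no ALP condition. Table 14 is presented as a screen for potential injury, not as a count of confirmed cases. Protocol 8.1 also has individual liver cases retested and followed during conduct. All of this stands, and it limits the consequence.

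It does not remove the point. The shift tables use the same grades and so need the same tie-break. Being a screen may excuse a false positive, but it is a weak defence for a row that can drop a concurrent case. The highest-severity convention in SAP 8.2.3 concerns adverse events and does not settle laboratory grades.

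A reader might go further in four ways that the documents do not support:

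- **That the counts are wrong.** The documents contain no results. Some counts are undetermined, and some rows can misclassify.
- **That there are three rival definitions.** There is one definition with an ambiguous *and*, plus two outputs that do not match it.
- **That low potassium is also double-graded.** Its Grade 2 keeps a numeric range once the italics are removed, and neither document prints a Grade 1 band to compare it with.
- **That the lower grade is the correct tie-break.** This is a preference, and it would make amylase Grade 4 unattainable. The higher grade would instead leave low-sodium Grade 2 empty.

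**Conclusion.** The point holds as three limited defects in the laboratory summaries.

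- Grades are undetermined for two tests, in three value ranges.
- The treatment-emergent definition, table and listing select different sets (5 strictly, or 8 to 11 inclusively; 6; and 8 to 11 of 25 grade pairs). Worsening from Grade 2 to 3 or from 3 to 4 is outside the tabulated count.
- The two combined liver rows can both over- and under-count concurrent abnormality. This assumes that the maximum rule governs the ALP condition as well, which is the natural reading of 8.3.3 but is not spelled out.

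How many patients are affected cannot be known from the documents. The reach is narrow. Table 14 works in multiples of ULN and baseline, so the grading overlap does not touch it. The adverse events of special interest come from coded terms and adverse-event grades (SAP Table 12). SAP 8 plans no inferential safety comparisons, and the primary endpoint is not involved. The points still deserve correction, because they decide what a named safety table reports and they are cheap to settle.

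**What to change.** 1. **SAP 8.3.2.** State one tie-break, lower or higher grade, for amylase above 2 × ULN and for sodium 125-129 mmol/L. Apply it in the shift tables, the treatment-emergent table and the listings, and note in the outputs which grade becomes unattainable as a result.
2. **SAP 8.3.1.** Define a treatment-emergent abnormality once, as a rise of at least 2 grades *or* any worsening from baseline to Grade 3 or 4 (8 of the 25 pairs). Use that definition in the text, the table and the listing.
3. **SAP 8.3.3.** Evaluate the two combined rows on the same sample, or take bilirubin within a stated number of days of the AST/ALT elevation with ALP from the AST/ALT sample. Keep the maximum-based eDISH plot and label it as the non-concurrent screen.

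The cost is programming specification only. No new data are needed, and no other analysis changes.
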